- To measure the incidence of SARS-CoV-2 infection documented by a positive PCR test during the study period.

Exploratory objectives:

- Proportion (95% CI) seroconverting to a positive response to SARS-CoV-2 IgG serology after two doses of vaccine, at 9 months, 12 months, 18 months, 24 months, 30 months, and 36 months after the second vaccine dose. This may mean that patients in routine healthcare have received one or more additional vaccine doses depending on the recommendations of the Public Health Agency of Sweden.
- To investigate the humoral response in more detail and analyze the cellular immune response after the vaccine has been administered.
- To examine the virus genome in breakthrough infections of SARS-CoV-2.
- To evaluate the significance of the oral and intestinal microbiome for vaccine efficacy in HIV-infected individuals.

Primary endpoint:

- Proportion (95% CI) seroconverting to a positive response to SARS-CoV-2 IgG serology test after two doses of vaccine, measured 2 weeks after the second vaccine dose.

Secondary endpoints:

- Proportion (95% CI) seroconverting to a positive response to SARS-CoV-2 IgG serology after two doses of vaccine, at 3 months and 6 months after the second vaccine dose.
- Proportion (95% CI) experiencing adverse events, including AE/SAE/SUSAR.
- Number and proportion (95% CI) who experience local reactions and systemic reactions.
- Proportion (95% CI) who receive a new diagnosis of SARS-CoV-2 infection through a positive PCR test.

Exploratory endpoints:

- Proportion (95% CI) seroconverting to a positive response to SARS-CoV-2 IgG serology after two doses of vaccine, at 9 months, 12 months, 18 months, 24 months, 30 months, and 36 months after the second vaccine dose.
- More detailed description of humoral and cellular immune responses at baseline and after vaccinations in blood and saliva at time points immediately before the first vaccine dose (day 0), day 10 after the first dose, immediately before dose 2 on day 21, and 2 weeks, 3 months, 6 months, 9 months, 12 months, 18 months, 24 months, 30 months, and 36 months after the second vaccine dose.
- Prevalence of escape mutations in SARS-CoV-2 sequencing in breakthrough infections.
- Prevalence of development/progression of graft versus host disease in allogeneic stem cell transplant recipients.
- Occurrence of biopsy-verified rejection in solid organ transplant recipients.

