All contact between study participants and study staff (research nurse or investigator) can be done remotely by telephone (or chat, if the Always Open function is available. Can also be done on site, if it coincides with the study participant's regular visit to the study unit, or if the study participant prefers to be sampled at the study unit). Blood samples can be taken at any of the Karolinska University Laboratory's sampling units in Stockholm, and saliva samples can be sent in a prepaid envelope to the Karolinska Institute.

- Review of concomitant medication (immunosuppressive/immunoglobulin treatments only).
- Sampling for SARS-CoV-2 IgG serology and more detailed analyses of humoral immunity (blood).
- Sampling for humoral immunity (saliva).
- Sampling for HIV-RNA and HIV-DNA for HIV-infected individuals.

Sampling group B

All procedures are performed at the study unit:

- Review of concomitant medication (immunosuppressive/immunoglobulin treatments only).
- Sampling for SARS-CoV-2 IgG serology and more detailed analyses of humoral immunity (blood).
- Sampling for humoral immunity (saliva).
- Sampling of HIV RNA and HIV DNA for HIV-infected individuals.

Sampling for analysis of cellular immunity (blood).

5.2.9. 9-month follow-up (9 m FU) after second vaccine dose (+/- 3 weeks)

New informed consent obtained before study procedure. Sampling group A

All contact between study participants and study staff (research nurse or investigator) can be done remotely by telephone (or chat, if the Always Open function is available. Can also be done on site, if coincides with the study participant's regular visit to the study unit, or if the study participant prefers to be sampled at the study unit). Blood samples can be taken at any of the Karolinska University Laboratory's sampling units in Stockholm, and saliva samples can be sent in a stamped envelope to the Karolinska Institute.

- Written informed consent regarding extended study
- Review of concomitant medication (only newly initiated immunosuppressive/immunoglobulin treatments).
- Note any additional vaccination with Comirnaty or other COVID-19 vaccination in the eCRF (concurrent treatment).
- Ask the study participant about COVID-19
- Sampling for SARS-CoV-2 IgG serology and more detailed analyses of humoral immunity (blood).
- Testing for humoral immunity (saliva).
- Sampling for HIV-RNA and HIV-DNA for HIV-infected individuals.

Sampling group B

All procedures are performed at the study unit:

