- Sampling for SARS-CoV-2 IgG serology and more detailed analyses of humoral immunity (blood).
- Testing for humoral immunity (saliva).
- Sampling of HIV-RNA and HIV-DNA for HIV-infected individuals.
- Fecal sampling for HIV patients and controls, for those individuals who have agreed to this part.

Sampling group B

All procedures are performed at the study unit:

- Review of concomitant medication (only newly initiated immunosuppressive/immunoglobulin treatments).
- Note any additional vaccination with Comirnaty or other COVID-19 vaccination in the eCRF (concomitant treatment).
- Ask the study participant about COVID-19
- Sampling for SARS-CoV-2 IgG serology and more detailed analyses of humoral immunity (blood).
- Sampling for humoral immunity (saliva).
- Sampling for HIV-RNA and HIV-DNA for HIV-infected individuals.
- Sampling for analysis of cellular immunity (blood).
- Fecal sampling for HIV patients and controls, for those who have agreed to this part.

5.2.13. 30-month follow-up (30 m FU) after second vaccine dose (+/- 3 weeks)

New informed consent obtained before study procedure. Sampling groups A
and B

All contact between study participants and study staff (research nurse or investigator) can be done remotely by telephone (or chat, if the Always Open function is available. Can also be done on site, if it coincides with the study participant's regular visit to the study unit, or if the study participant prefers to be sampled at the study unit). Blood samples can be taken at any of the Karolinska University Laboratory's sampling units in Stockholm, and saliva samples can be sent in a stamped envelope to the Karolinska Institute.

- Review of concomitant medication (only newly initiated immunosuppressive/immunoglobulin treatments).
- Note any additional vaccination with Comirnaty or other COVID-19 vaccination in the eCRF (concurrent treatment).
- Ask the study participant about COVID-19.
- Sampling for SARS-CoV-2 IgG serology and more detailed analyses of humoral immunity (blood).
- Sampling for humoral immunity (saliva).
- Sampling of HIV-RNA and HIV-DNA for HIV-infected individuals.

Study participants will receive a SARS-CoV-2 antigen test kit for saliva sampling in case of COVID symptoms. Study participants will only contact the research staff if they test positive or need more test kits.

5.2.14. 36-month follow-up (36 m FU) after second vaccine dose (+/- 3 weeks)

Sampling group A

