5.4.8. Study participants with a new diagnosis of COVID-19 during the study period

If the patient receives a virologically confirmed COVID-19 diagnosis in healthcare outside the study, this information, including the date of a positive test, will be collected from the study participant's medical records. The presence of a diagnosis of pneumonia or thromboembolic complications in connection with COVID-19 will be noted, as well as any treatment given for COVID-19 or complications. Sequencing will be performed on the PCR sample.

The severity of COVID-19 will be graded using the highest degree reached on the scale during the period of illness (no later than 4 weeks after symptom onset), according to the following ordinal scale (Beigel JH et al., 2020):

1. Not hospitalized, with no restrictions on activities.
2. Not hospitalized, but with restrictions on activities and/or need for oxygen therapy at home.
3. Admitted to hospital, but does not require extra oxygen and no longer needs ongoing medical care.
4. Hospitalized and does not require oxygen therapy, but requires ongoing medical care.
5. Hospitalized and requires oxygen therapy.
6. Hospitalized with a need for noninvasive ventilation (NIV) or high-flow oxygen therapy.
7. Hospitalized with mechanical ventilation or ECMO (extracorporeal membrane oxygenation) treatment.
8. Death.

Table 2: Overview of study design for study participants receiving Comirnaty

Visit No.	Screening	1	2	3	4	5	6	7	8	9	10	11	12	13
Administration Comirnaty		dose 1		dose 2										
Study contacts		d 0	10 d FU (vacc 1)	d 21	2 weeks FU (vacc 2)	6 weeks FU (vacc 2)	3 months FU (vacc 2)	6 months FU (vacc 2)	9 months FU (vacc 2)	12 months (vacc 2)	18 months (vacc 2)	24 months (vacc 2)	30 months (vacc 2)	36 months (vacc 2)
Time span	0-28 days before visit 1	Day 0	+/-3 days	+/-3 days	+/-3d	+/-3d	+/- 2 w	+/- 3v	+/- 3v	+/- 3v	+/- 3v	+/- 3 weeks	+/- 3v	+/- 3v
Contacts and sampling¹ for sampling group A without cellular analyses														
Study visits to the study unit		X		X										
Remote contact (telephone/chat) by nurse/tester			X		X	X								
Review of health declaration questions in Vaccinate and/or registration in Vaccinate			X		X									
Sampling of clinical laboratory samples	X ¹	(X) ^{1,2}		X _{1,2}	X ¹									
SARS-CoV-2 serology and extended humoral immunity sampling immunity (blood and saliva)		X ²	X ³	X ²	X ³		X ³	X ³	X ³	X ³	X ³	X ³	X ³	X ³
Contacts and sampling¹ for sampling group B with cellular analyses														

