5.9.7. Discontinuation criteria

Participants may choose to withdraw from the study at any time without giving a reason. Specific grounds for **discontinuation of study treatment**

- The participant withdraws their consent
- Participants who do not meet the compliance requirements
- If SUSAR, SAE, severe AE, or other medical condition arises, where continued study participation could pose a risk to the participant, in the investigator's judgment, the study drug treatment will be discontinued. The participant will then be offered medical follow-up within the framework of the study.
- Participants who become pregnant during the study
- Severe/systemic allergic reaction to the vaccine.
- The patient has not completed follow-up (lost to follow-up).
- The investigator has the right to discontinue participation in the study if there are reasons that may affect the individual's safety.
- The relevant authority may terminate the study

If an individual withdraws, information collected during the time they were participating in the study will be used to perform the analyses described. A follow-up visit will be offered to individuals who have discontinued their participation.

No Data and Safety Monitoring Committee (DSMC) is planned to be established in this open-label, non-randomized study. This is because Comirnaty has already been studied in approximately 21,000 individuals regarding its safety profile. This is an open-label study, and we do not expect an increased number of AE/SAE/SUSAR in primary populations.

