6.2. Analysis populations

Population	Description of population
Full analysis set population	All study participants who have received at least one dose of vaccine
Population with two doses of vaccine	All study participants who received two doses of vaccine and had a test result at 2 weeks after the second vaccine dose.
Population with evaluable reactogenicity after dose 1	All study participants who have received at least one dose of vaccine and have at least one measurement of reactogenicity after the first dose.
Population with Evaluable reactogenicity after dose 2	All study participants who have received two doses of vaccine, and had at least one measurement of reactogenicity after the second dose.

The number and percentage of study participants who are enrolled in the study, complete the study, and discontinue the study will be presented. Reasons for discontinuation will also be presented.

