6.3.3. Analyses of secondary endpoints

- Proportion (95% CI) seroconverting to a positive response to SARS-CoV-2 IgG serology after two doses of vaccine, at 3 months and 6 months after the second vaccine dose, measured in the "two-dose vaccine population" compared with the control group.
- Proportion (95% CI) experiencing adverse events, with AE/SAE/SUSAR. Number and proportion (95% CI) experiencing local reactions and systemic reactions are measured in the "Full analysis set population".
- Proportion (95% CI) receiving a new diagnosis of SARS-CoV-2 infection through a positive PCR test is measured in the "Full analysis set population."

- Comparisons are made with the control group.

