8.3 Procedure for obtaining informed consent

The principal investigator at each trial site shall ensure that the research subject is given full and adequate verbal and written information about the study, its purpose, any risks and benefits, and inclusion/exclusion criteria. Research subjects must also be informed that they are free to withdraw from the study at any time without having to give a reason. The research subject shall be given the opportunity to ask questions and be allowed time to consider the information provided. If the person chooses to participate, the research subject and the investigator shall sign the consent form. A copy of the research subject information and the signed consent form shall be given to the research subject. The research subject's signed and dated informed consent must be obtained before any study-specific activity is performed in the study. Each research subject participating in the study will be identified by a research subject number on a research subject identification list. The research subject consents to monitors and inspectors having access to their medical records and other source data. If new information becomes available during the study, the research subject has the right to reconsider whether he/she wishes to continue participating.

In this study, informed consent may be signed on paper forms or electronically with Bank ID. The study population also includes English-speaking research subjects. These subjects will be informed in English and will sign an English version of the informed consent form. Signed informed consent for participation in the two extension parts of the study will be obtained before sampling begins.

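### The infection endpoint is a crude proportion with no time window or time-at-risk rule, so it can understate risk and can distort the comparison with controls if follow-up differs

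*Combined protocol and SAP*

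**What the plan says.** The secondary objective (Synopsis and section 4.1) is "To measure the incidence of SARS-CoV-2 infection documented by a positive PCR test during the study period". Section 6.3.3 turns this into a single figure: "Proportion (95% CI) receiving a new diagnosis of SARS-CoV-2 infection through a positive PCR test is measured in the" full analysis set. Section 6.2 defines that set as "All study participants who have received at least one dose of vaccine". Section 6.3.3 adds a comparison with the control group, and section 6.4 names the chi-square test for comparing patient groups with controls.

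Scheduled visits run to 36 months after dose 2 (section 5.2.14). Sections 5.2.9 (month 9) and 5.2.13 (month 30) both carry the line "New informed consent obtained before study procedure", and section 8.3 says: "Signed informed consent for participation in the two extension parts of the study will be obtained before sampling begins".

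On withdrawal, section 5.9.7 says: "If an individual withdraws, information collected during the time they were participating in the study will be used to perform the analyses described". Section 5.4.8 provides that if a participant has a "virologically confirmed COVID-19 diagnosis in healthcare outside the study, this information, including the date of a positive test, will be collected" from the medical records.

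For this endpoint, section 6 gives no time window, no end of time at risk, no censoring rule, no treatment of death and no missing-data rule.

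**The concern.** A proportion of everyone dosed is a risk only if everyone is observed for the same stated period. Here the period is unstated and equal observation cannot be presumed. Participants can decline at either of two consent points, withdraw or die. The patients have serious underlying disease, while section 5.1.3 requires controls to have no significant co-morbidity.

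The denominator is fixed at dose 1. A later infection that the study does not learn of therefore adds nothing to the numerator, while the person stays in the denominator. Two things follow:

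- Each group's proportion can be too low, and it is not the risk at any named time.
- If patients and controls are observed for different lengths of time, the chi-square test compares follow-up as well as infection. Patients who leave more often could look better protected than they are. If controls leave more often, the error runs the other way.

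**Working it through.** **Plan's own figure.** None exists for this endpoint. The power statement in section 6.1 concerns seroconversion only.

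**Inputs from the documents.** 450 patients and 90 controls (section 5.1.1); consent points at months 9 and 30; last scheduled visit at month 36.

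**Assumptions, because the documents give no rates.** True 36-month infection risk of 30% in both groups, constant hazard, and no capture of infections after exit. For simplicity, time runs on one 36-month scale.

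**Step 1: risk by each exit point.** F(t) = 1 − 0.7^(t/36).
- F(9) = 1 − 0.7^0.25 = 8.5%
- F(30) = 1 − 0.7^(30/36) = 25.7%
- F(36) = 30%

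**Step 2: expected crude proportion when a fraction L leaves at month 9.** P = L × F(9) + (1 − L) × F(36).
- L = 0.10: 0.10 × 8.53% + 0.90 × 30% = 27.9%
- L = 0.20: 0.20 × 8.53% + 0.80 × 30% = 25.7%
- L = 0.30: 0.30 × 8.53% + 0.70 × 30% = 23.6%

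With 10% of controls and 30% of patients leaving, the false gap is 27.9 − 23.6 = 4.3 points. If a further 20% of those remaining leave at month 30, the proportions are 27.1% and 23.0%. If both groups lose the same fraction, both proportions fall equally and there is no false gap.

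**Step 3: gap against sampling error.** At 30% risk, SE = sqrt(0.30 × 0.70 × (1/450 + 1/90)) = sqrt(0.0028) = 5.3 points. The gap is 4.3/5.3 = 0.8 standard errors. For one patient group of 90 against 90 controls, SE = sqrt(0.21 × 2/90) = 6.8 points and the gap is 0.6 standard errors.

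**Step 4: other assumed rates.** Exit is now at both consent points, the month-30 figure being a fraction of those remaining. True risk is equal in both groups throughout.

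| Assumed 36-month risk | Exits, controls | Exits, patients | Crude, controls | Crude, patients | Crude risk ratio |
|---|---|---|---|---|---|
| 40% | 20%, 10% | 20%, 10% | 34.0% | 34.0% | 1.00 |
| 40% | 10%, 5% | 30%, 10% | 37.0% | 31.2% | 0.845 |
| 40% | 30%, 10% | 10%, 5% | 31.2% | 37.0% | 1.18 |

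In the second row, the 450-against-90 chi-square test rejects with probability 19% instead of 5%. With risks of 20% to 60%, control exits held at 10% and 5%, and patient exits of 20% to 40% at month 9 and 10% to 20% at month 30, the crude risk ratio runs from 0.75 to 0.93 and the rejection probability from 7% to 58%. If controls leave more, as in the third row, the ratio over the same risks is 1.17 to 1.19. The rate ratio per person-time is 1.00 in every case.

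**Step 5: calendar.** The Synopsis puts last inclusion in Q2 2022 and last completion in Q2 2024, about 24 months apart. That cannot hold a 36-month visit for the last participants. If those dates stand, follow-up is unequal even without dropout. Under the Step 1 assumptions, risk at 24 months is 1 − 0.7^(24/36) = 21.2%, against 30% at 36 months.

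**The case against.** A reader might infer that the plan scores leavers as uninfected and that the comparison is therefore biased. The documents do not go that far, for four reasons.

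- **No such scoring rule is written.** It is a default consequence of a fixed denominator. Infections before exit do count. PCR testing is prompted by symptoms (section 5.3.5), and positives diagnosed elsewhere are taken from medical records with their dates (sections 5.4.8 and 5.5.10). Consent for the extensions is tied to sampling, so record capture might continue. This stands as a limit on the size of the problem. It does not remove it, because the plan does not say that capture continues after withdrawal or declined consent.
- **The 36-month window is inferred.** Seroconversion is a secondary endpoint only to month 6 and exploratory from month 9. If the infection endpoint followed the same division, neither consent point would fall inside its window and the illustration above would not apply. In favour of the longer reading, section 9 ends the study at the last participant's final follow-up, and PCR testing sits among the procedures for the entire study period (section 5.3). Neither passage settles the analysis window, which is why the plan needs to state it.
- **A false gap needs unequal observation.** No exit rates are given. The patients attend regular check-ups at the same hospital, so controls could be the group that leaves more. The direction is unknown.
- **The setting is modest.** This is a secondary endpoint in a study that section 6.1 describes as descriptive or exploratory, and discontinuations will be reported with reasons (section 6.2). The 4.3-point gap is within one standard error.

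The contrast between incidence in the objective and a proportion in the analysis carries little weight alone, because the protocol also speaks of the incidence of seroconversion and measures it as a proportion.

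**Conclusion.** The point holds as a gap in the analysis plan that should be closed. Followed as written, the analysis gives a proportion tied to no stated time, and that proportion is too low whenever later infections are missed. The comparison with controls can be biased, in an unknown direction, if observed time differs between groups. With equal exit and equal risk it is not biased.

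The 4.3-point gap (27.9% against 23.6%) illustrates the mechanism. It does not estimate what will happen in this study. It rests on a 30% risk over 36 months in both groups, constant hazard, exits of 10% against 30% at month 9, and no capture after exit. None of these comes from the documents, and any capture from records after exit would shrink the gap.

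**What to change.** In sections 4.2 and 6.3.3:

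1. State the window for the infection endpoint and when time at risk ends: withdrawal, declined re-consent if record capture stops then, death, or last contact or record check. Say whether record capture continues after a participant leaves or declines re-consent.
2. Analyse time from dose 1 to first positive PCR. Report cumulative incidence with 95% CI at fixed times, for example 6, 12 and 24 months, and 36 if the window extends that far. Treat death as a competing event and use the Aalen-Johansen estimator. Kaplan-Meier with deaths censored would not do this. Rates per person-year with 95% CI are an acceptable alternative.
3. Replace the chi-square test for this endpoint with a comparison on the chosen scale.
4. State that censoring at exit assumes exit is non-informative.
5. State that detection changes from month 30, when participants receive home antigen kits and contact staff only if positive or needing more kits (sections 5.2.13 and 5.2.14), while the endpoint requires PCR.
6. Reconcile the Synopsis dates with the 36-month schedule.

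The cost is SAP wording, slightly more analysis work and one added assumption, that of item 4. The dates of positive tests are already collected.

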5.1.3. Inclusion criteria

1. Individuals who are ≥ 18 years old.
- 2a. Individuals with immunosuppressive disease who meet one of the following criteria:
 - Primary immunodeficiency

- HIV infection
- Review of allogeneic stem cell transplantation/CAR T cell therapy
- Review of solid organ transplantation
- Chronic lymphocytic leukemia

or

2b. Individuals without immunosuppressive disease or treatment who, in the investigator's opinion, have no significant co-morbidity.

3. Signed written consent to participate in the study.

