5.7. Definitions of adverse events

5.7.1. Incident/Adverse event (AE)

Any incident (AE), or worsening of an existing medical condition in a research subject who has received an investigational drug, regardless of whether it is causally related to the treatment or not, i.e., it may be an adverse and undesirable sign (including an abnormal laboratory finding), symptom, or disease that is temporally associated with the use of an investigational medicinal product, regardless of whether it is related to the investigational medicinal product or not.

However, events that are an expected consequence of the underlying disease, such as worsening of the underlying disease, will not be reported as an AE. This is because we do not expect Comirnaty to affect the progression of the underlying disease.

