5.7.2. Serious incident/Serious adverse event (SAE)

Any incident that:

- results in death
- is life-threatening
- requires hospitalization or prolongs hospitalization
- causes permanent or significant disability or impairment
- results in a congenital injury/malformation
- is serious for other reasons as described below

Medical and scientific judgment should be used to determine whether an event is "serious" and whether it would be reportable in other situations, such as important medical events that may not be directly life-threatening or result in death or hospitalization, but may jeopardise the research subject or may require intervention to prevent one of the other outcomes listed in the definition above. These should also be considered SAEs.

However, events that are an expected consequence of the underlying disease, such as worsening of the underlying disease, will not be reported as SAEs. This is because we do not expect Comirnaty to affect the progression of the underlying disease.

Hospitalization due to day surgery, elective surgery, or admission that was planned before the start of the study for a pre-existing medical condition that has not worsened

is not considered an SAE.

The investigator is responsible for assessing the severity (serious or non-serious). If the incident is considered serious, it should be reported as a serious adverse event (SAE) by the investigator to the sponsor.

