5.9. Reporting of adverse events

5.9.1. Reporting of adverse events (AE)

- All adverse events should be recorded in a special AE form in the CRF for the period from the day of the first and second vaccine doses until 14 days after each vaccine dose. Exceptions are adverse events that are an expected consequence of the underlying disease, such as worsening of the underlying disease.
- Rationale for the above point: In Phase I and Phase II/III studies of Comirnaty, AEs were collected for the period from informed consent to one month after the second dose. As this has already been studied in approximately 21,000 people with a favorable safety profile, and we do not expect multiple AEs or autoimmune reactions in immunosuppressed individuals, the observation periods are limited to those above. As we expect frequent medical events of a non-serious nature in the majority of the included primary population due to the existing medical condition, such events are excluded from data collection.

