5.9.2. Reporting of serious adverse events (SAEs)

- All serious adverse medical events (SAEs) must be noted in the CRF for the period from the first vaccine dose to 6 weeks after the second dose. Exceptions are medical events that are an expected consequence of the underlying disease, such as worsening of the underlying disease.

- SAEs must be reported to the sponsor on a special SAE form within 24 hours of the investigator becoming aware of the SAE. Follow-up information describing the outcome and management of the SAE must be reported as soon as that information is available. The original must be entered in the CRF.
- Rationale for the above points: In Phase I and Phase II/III studies of Comirnaty, SAEs were collected for the period from informed consent to six months after the second dose. As this has already been studied in approximately 21,000 people with a favorable safety profile regarding SAE, and we do not expect multiple SAE or autoimmune reactions in immunosuppressed individuals, the observation periods are limited to those above. As we can expect serious medical events in the majority of the included primary population due to the existing medical condition.

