6.4. Statistical methods

Continuous variables will be presented with mean and standard deviation [SD] for normally distributed values, and median and interquartile range (IQR) for non-normally distributed values. Categorical variables will be presented as frequency distributions.

Comparisons between patient groups and the control group will be made using the Chi-square test. P-values will be adjusted for multiple comparisons where necessary.

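### AE/SAE/SUSAR proportions are tested against controls although a recording exemption that acts almost only on patients makes the two numerators follow different rules

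*Combined protocol and SAP*

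**What the plan says.** Section 6.3.3 gives the safety endpoint as "Proportion (95% CI) experiencing adverse events, with AE/SAE/SUSAR", measured in the full analysis set, and ends its list of secondary analyses with "Comparisons are made with the control group". Section 6.4 names the method: "Comparisons between patient groups and the control group will be made using the Chi-square test".

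What counts as an event is set elsewhere. Section 5.7.1: "However, events that are an expected consequence of the underlying disease, such as worsening of the underlying disease, will not be reported as an AE". Section 5.7.2 has the matching rule: "However, events that are an expected consequence of the underlying disease, such as worsening of the underlying disease, will not be reported as SAEs". Section 5.9.1 repeats it for the AE form: "Exceptions are adverse events that are an expected consequence of the underlying disease, such as worsening of the underlying disease". Sections 5.9.2 and 5.9.3 carry the same exception for SAE and SUSAR entries in the CRF.

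The rationale in 5.9.1 refers to frequent non-serious events caused by the existing condition in most of the primary population, and says these are left out of data collection. The parallel sentence in 5.9.2 is incomplete: "As we can expect serious medical events in the majority of the included primary population due to the existing medical condition".

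Controls are defined in 5.1.3 as "Individuals without immunosuppressive disease or treatment who, in the investigator's opinion, have no significant co-morbidity".

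**The concern.** A comparison of two proportions needs an event to mean the same thing in both groups. Here an investigator's attribution to underlying disease removes an event before it reaches the CRF, and only patients have a substantial underlying disease to attribute it to. Section 6 contains no attribution flag, sensitivity analysis or caveat, and an unrecorded event cannot be restored at analysis.

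This bears on a stated question. Safety and tolerability is a secondary objective, and the synopsis says it is unclear whether immunosuppressed people differ from healthy people in side effects. The exemption rests on the expectation that the vaccine will not affect the underlying disease. Yet section 4.2 makes GVHD progression, biopsy-verified rejection and HIV viremia exploratory endpoints, which treats that expectation as open. Those endpoints do not feed the AE/SAE proportions, and primary immunodeficiency and CLL have no equivalent.

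**Working it through.** The plan states no expected AE or SAE rate, no exempt share and no power for this comparison, so there is no figure to reproduce. From the documents: 450 patients in five groups of 90, 90 controls (5.1.1), chi-square (6.4), alpha 0.05 (6.1). All event rates below are assumptions.

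**1. Path of an event into the numerator**

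| Event | Patient | Control |
|---|---|---|
| Unrelated to any disease | counted | counted |
| Background event of the immunosuppressive disease | not recorded | does not arise |
| Vaccine-triggered, attributed to underlying disease | not recorded | counted, since there is almost no disease to attribute it to |
| Solicited diary reaction (5.5.3, 5.8.3) | diary, no exemption stated | diary, no exemption stated |

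**2. Direction.** Let s be the share of patients with an event whose events are all exempt. Then

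observed patient proportion = full-recording proportion × (1 − s).

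For any s > 0 this falls, while the control proportion is essentially unchanged. For full-recording proportions of 5% to 40% and s of 10% to 50%, the fall runs from 0.05 × 0.10 = 0.5 percentage points to 0.40 × 0.50 = 20 points. The range is wide because the documents fix neither input.

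**3. What each count measures.** Assume independent components: 10% background events unrelated to disease and 10% vaccine events in everyone; 20% background disease events in patients only; and a share f of patients with a vaccine-triggered event attributed to their disease.

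- Controls: 1 − 0.9 × 0.9 = 19%.
- Patients under the exemption: 1 − 0.9 × 0.9 = 19%, whatever f is.
- Patients, vaccine-attributable contrast: 1 − 0.81 × (1 − f).
- Patients, all-cause: 1 − 0.81 × 0.8 × (1 − f).

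| f | True vaccine-attributable difference | Shown under the exemption | Shown with all-cause counting |
|---|---|---|---|
| 0 | 0 | 0 | 35.2% − 19% = +16.2 points |
| 5% | 23.05% − 19% = +4.05 points | 0 | 38.44% − 19% = +19.4 points |
| 10% | 27.1% − 19% = +8.1 points | 0 | 41.68% − 19% = +22.7 points |

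The exemption gives the right answer only when f = 0, and all-cause counting is wrong in every row.

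**4. What a test on all-cause counts would do.** Assume a shared 20% risk plus an independent 20% of disease events in patients, with no vaccine difference. Patients then have 1 − 0.8 × 0.8 = 36% against 20%. A 5% chi-square test declares patients worse in 87% of trials at 450 v 90 and 67% at 90 v 90. Under the exemption the comparison is 20% v 20%, and a false result in either direction occurs at about the nominal 2.5%.

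**The case against.** The strongest defence is that the exemption does useful work. The groups are not randomised and patients carry a heavier burden of illness. Removing background disease events removes a confounder, as step 4 shows. This stands, and it is why simply counting everything and keeping the test is no remedy. It does not cover vaccine-triggered events attributed to the disease, which are lost on one side only.

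Section 6.1 also calls the study descriptive or exploratory, and no safety hypothesis or margin is stated. That limits the weight of the point, but sections 6.3.3 and 6.4 still plan the comparison and its test.

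Four stronger readings are tempting and should be resisted.

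- **That the exemption will often make patients look significantly safer.** With 20% all-cause risk in both groups and half of patient events exempt, the comparison becomes 10% v 20%, and patients are declared safer in 73% of trials at 450 v 90 (47% at 90 v 90). This assumes equal all-cause risk, which the rationale in 5.9.1 contradicts. In that scenario, moreover, patients' non-disease risk really is lower.
- **That more than 225 of 450 patients have uncounted serious events, against 0 of 90 controls.** The sentence in 5.9.2 is an incomplete rationale with no time window, not a forecast for the reporting period.
- **That nothing can be removed for controls.** Only significant co-morbidity is barred. Appendix 1 records controls' diagnoses, and the exemptions for existing conditions in 5.5.5 and 5.5.7 apply to everyone. The asymmetry is near-complete, not absolute.
- **That the exemption could by itself produce the milder reactions the protocol expects.** Sections 2.2 and 3.2, and largely 5.3.2, speak of reactogenicity, which comes from the diary and is untouched.

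**Conclusion.** The concern holds in a limited form. The AE/SAE/SUSAR proportions compared in 6.3.3 follow different counting rules in patients and controls. Relative to full recording, the exemption can only lower the patient proportion, and it can hide vaccine-triggered events attributed to disease in patients while almost no such loss is possible in controls. The size cannot be derived from the documents; the 4-point and 8-point losses above rest on assumed rates and independence. All-cause counting errs in the other direction. A significant or a null chi-square result on overall AE/SAE/SUSAR would therefore not be interpretable as a difference in vaccine safety. The solicited-reaction comparison remains sound on this point. The matter concerns a secondary endpoint and should be corrected, but it does not affect the primary analysis.

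**What to change.** In 6.3.3, remove the chi-square comparison with controls for overall AE/SAE/SUSAR. Report those proportions by group with 95% CI, labelled as omitting events attributed to underlying disease. Keep the tested comparison for solicited local and systemic reactions, which are collected in the same way in both groups. This changes analysis wording only and remains possible after data collection. Its cost is that there is no tested overall AE/SAE comparison.

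If a tested comparison of unsolicited events is wanted, 6.3.3 alone is not enough, because the exempt events are never recorded. Sections 5.7 and 5.9 and the CRF would have to require all events in both groups to be recorded with a causality grade and an underlying-disease flag. The analysis would then compare probably or possibly related events and show results with and without flagged events. This costs more event recording and leaves fewer events in the test. It also relies on open-label causality grading whose categories in 5.8.2 themselves refer to underlying disease, so some asymmetry would remain.
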